5.0 Special Considerations

5.1 Health Insurance Portability and Accountability Act (HIPAA)

PHI (name: for tracking reimbursement with gift cards) This will be kept in a separate document. Participants age and health condition is part of the data set. It will only be included with the single data set that is used to generate the study codes.

5.2 Family Educational Rights and Privacy Act (FERPA): NA

5.3 Code of Federal Regulations Title 45 Part 46 (Vulnerable Populations): NA

A. Special Populations

5.4 General Data Protection Regulation (GDPR): NA

5.5 NJ Access to Medical Research Act (Surrogate Consent): NA

6.0 Data Management Plan

6.1 Data Analysis

Power analysis was described under sample calculation

Aim / Dependent variable	Factor(s)	Test
Aim 1 – Exercise Intensity		
Cycling Cadence (baseline-adjusted)	condition (feedback & 2 competition conditions)	Repeated measures ANOVA (Rm-ANOVA)

		Post-hoc paired t-tests with appropriate Bonferroni corrections
Heart Rate (age-adjusted)	condition (feedback & 2 competition conditions)	Rm-ANOVA Post-hoc paired t-tests with appropriate Bonferroni corrections
AIM 2 – User Experience of Exercise		
Rating of Perceived Exertion (RPE)	condition (feedback & 2 competition conditions)	Rm-ANOVA Post-hoc paired t-tests with appropriate Bonferroni corrections
Motivation (custom IMI Scale)		
Interest/Enjoyment Perceived Competence Effort/Importance Value/Usefulness	condition (feedback & 2 competition conditions)	Rm-ANOVA Post-hoc paired t-tests with appropriate Bonferroni corrections
AIM 3 - Attention		
Eye-Tracking Data Dwell Time Percentage	condition (feedback & 2 competition conditions)	Rm-ANOVA Post-hoc paired t-tests with appropriate Bonferroni corrections

Bold = Primary comparison Co-variates (exercise readiness, competitiveness, and physical activity) may be included in an ANCOVA analysis. Analysis is simple to parse individual effects and then explore the moderating effects of the cycling condition. Due to the sample size, we will not attempt to impute for missing measures. Analyses will be carried out with all available data for each one of the planned comparisons.

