1.0 Research Design

1.1 Purpose/Specific Aims

The short-term goal of this project is to gain insight into specific strategies of VR-based rehabilitation to increase motivation and intensity for persons with PD during a cycling task. **The long-term goal of this study is to determine the essential elements in designing a training circuit for persons with PD to promote mobility and fitness resulting increased activity and participation.** The short-term goals will be achieved through two primary aims that build upon the parent grant (1-2) and further refined through a mechanistic aim about the role of attention in explaining behavior in the VE (3).

We aim to build upon our work in PD and that of others in persons post stroke by using augmented visual feedback and competition to increase exercise intensity and motivation while cycling in a virtual environment.

Aim 1: Determine the effect of visual feedback and competition (self or others) during virtual bicycling on neuromuscular (cycling cadence) and cardiovascular (% max heart rate) intensity

Hypothesis: Competition will produce higher neuromuscular and cardiovascular intensity compared to feedback.

Aim 2: Determine the effect of visual-feedback and competition (self or others) during virtual bicycling on the user experience of motivation & enjoyment (Intrinsic Motivation Inventory: IMI) & perception of exercise intensity (Borg Scale)

Hypotheses: Competition will elicit a higher motivation and enjoyment compared to visual feedback. Competition will result in lower perceived exertion compared to visual feedback.

Aim 3: Determine if attention differs (dwell time percentage) in augmented visual feedback bicycling compared to competition (self or others) virtual bicycling

Hypothesis: Attention will be higher during competition virtual bicycling when compared to augmented bicycling.

A. Objectives (see above)

B. Hypotheses / Research Question(s) (see above)

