1.5 Sample Size Justification

Power analyses- Sample size for **Aim 1**: An a priori power analysis was powered upon preliminary cycling cadence data published from the lab. [15] The power analysis conducted in G*Power, [20] determined that 19 participants would be required to reach a power level of 0.80 (Cohen's D =0.7, moderate effect size). **Aim 2**: An a priori power analysis powered on motivation and enjoyment (Intrinsic Motivation Inventory) [21] with an effect size of 0.75 determined that 16 participants would be required. This effect size was adapted from Cikajilo & Potisk 2019, who investigated a fine motor upper extremity task for persons with PD in a fully-immersive environment. We used their reported average effect size of the different IMI subscales. [22] **Aim 3**: There are no pilot data (collected by our team or published by others) for this aim. An effect size will be calculated from these data to power future studies. Considering all the sample size calculations and accounting for a 20% attrition rate, 24 participants will be required for this study.

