1.6 Study Variables

A. Independent Variables, Interventions, or Predictor Variables

Cycling Mode (Visual feedback versus competition against self and others)

B. Dependent Variables or Outcome Measures

See table below (*Table 1*):

Neuromuscular Exercise Intensity	
Cycling cadence	Measured by the Wahoo sensor on the bicycle crank. Referenced to the self-selected cadence to measure the % increase as well as the absolute value (Aim 1)
Cardiovascular Exercise Intensity	
Heart Rate (HR) % of maximum	Collected with Garmin or Polar HR monitor worn on the forearm. Referenced to age maximum and interpreted as a percent (Aim 1)
Blood pressure (BP)	Collected manually with upright Braum mercury sphygmomanometer (Aim 1)
Perceived Effort	
Rating of perceived exertion (RPE)	The Borg Scale of perceived Exertion will be used to collect this information. The lowest measure on the scale is 6: no exertion at all, and the highest is 20: maximal exertion (Aim 2)
Open Ended Questions	Ranking of 3 conditions and interview for qualitative data (Aim 2)
Motivation	
Intrinsic Motivation Inventory (IMI)	Customized motivation inventory capturing 4 constructs including: interest & enjoyment, perceived competence, effort & importance, value & usefulness. Participants will complete the IMI after each condition. The IMI has been validated for older adults (Aim 2)
Open Ended Questions	Ranking of 3 conditions and interview for qualitative data (Aim 2)

HRP-503a - TEMPLATE - Interventional Research Protocol 1.1.21

Protocol Title: Enhancing Exercise Intensity, Motivation and Enjoyment for Persons with PD (VCycle-Competition)

Protocol Version Date: v5 1.18.23;

Protocol # - Pro2021001412

Attention	
Eye-Tracking Data	Collected continuously at 30-50 Hz with HTC Vive Pro Eye, using built-in Tobii infrared eye-trackers. Data will be collected and analyzed from 1 minute until the end of the bicycling bout to account for acclimation to the VE
Participant Characteristics	
UPDRS Motor Score Section III	To quantify motor involvement & disease severity
Physical Activity Scale for the Elderly (PASE)	To measure participants physical activity at time of testing (can be used to classify individuals as high and low exercisers. Used and validated to measures activity in persons with PD May be used as a co-variate
Simulator Sickness Questionnaire (SSQ)	To measure adverse events in the immersive virtual environment. Has been used to measure simulator sickness in persons with PD

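### Four IMI subscales serve one Aim 2 motivation hypothesis with no stated rule across them, and the Aim 2 sample size is for a test that section 6.1 does not plan

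*Combined protocol and SAP*

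**What the plan says.** Section 1.1 gives Aim 2 a single motivation hypothesis: "Competition will elicit a higher motivation and enjoyment compared to visual feedback". The Table 1 entry in section 1.6 describes the IMI as a "Customized motivation inventory capturing 4 constructs including: interest & enjoyment, perceived competence, effort & importance, value & usefulness", and no total score is named there.

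In section 6.1 the motivation row lists "Interest/Enjoyment Perceived Competence Effort/Importance Value/Usefulness". The factor is "condition (feedback & 2 competition conditions", so there are three conditions and three possible pairs per subscale. The test is a repeated-measures ANOVA followed by "paired t-tests with appropriate Bonferroni corrections". The divisor, the alpha level and the sidedness are not stated. The table's legend reads "Bold = Primary comparison", but type weight did not survive in the text available to this review.

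Section 1.5 powers Aim 2 on the IMI at an effect size of 0.75 and "determined that 16 participants would be required". The 0.75 comes from a cited study of an upper-limb task: "We used their reported average effect size of the different IMI subscales".

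**The concern.** One hypothesis with four chances to succeed needs a rule. The visible text does not say whether one positive subscale is enough, whether all four are needed, or whether one of them decides. A significant result on any subscale could therefore be offered as support. A split result, such as enjoyment up and perceived competence down, has no agreed reading.

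The sample-size sentence does not settle this. It uses an average over subscales, which suggests that no single subscale was chosen to carry Aim 2. It also corresponds to one unadjusted two-condition comparison, whereas section 6.1 plans a three-condition ANOVA and then corrected pairs.

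**Working it through.** **Inputs from the documents.** Four subscales and three conditions (6.1). Aim 2 effect size 0.75 and N = 16; Aim 1 effect size 0.7, power 0.80 and N = 19; 20% attrition and 24 enrolled (1.5).

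**Assumptions.** Alpha 0.05, with two-sided paired tests; power 0.80 for Aim 2, as stated for Aim 1; correlation between subscales 0 to 0.7, which the documents do not give; normally distributed scores.

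**Step 1: reproduce the plan's figures.** For a paired t-test with n completers, power = P(|T| > t(1−α/2; n−1)), where T is noncentral t with n−1 degrees of freedom and noncentrality d√n.

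- Aim 2: 0.75 × √16 = 3.00, power 0.801. N = 16 is reproduced.
- Aim 1: 0.7 × √19 = 3.05, power 0.823. N = 19 is reproduced.
- Enrolment: 19 / 0.80 = 23.75, rounded up to 24.

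One-sided 0.05 would give 13 and 15 instead of 16 and 19, so two-sided 0.05 is the natural inference.

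**Step 2: false positives with no true effect.** If the four omnibus tests are independent, P(at least one significant) = 1 − 0.95⁴ = 0.185. For correlated subscales this was simulated (60,000 trials per setting): an ANOVA at 0.05 per subscale, then paired t-tests at two-sided 0.05/3. Results for 19 completers:

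| Event | One subscale | Four, corr. 0 | Four, corr. 0.5 | Four, corr. 0.7 |
|---|---|---|---|---|
| Any omnibus effect, any direction | 5% | 18.7% (exact 18.5%) | 16.1% | 13.4% |
| Omnibus plus a corrected pair with competition above feedback | 1.2% | 4.8% | 4.3% | 3.5% |

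Runs with 24 completers gave nearly the same values (13.6% and 3.6% at correlation 0.7). The multiplication for the directional claim is 4.8/1.2 = 4.0 at correlation 0 and 3.5/1.2 = 2.9 at 0.7. If the pairs are read without first requiring a significant omnibus test, the four-subscale directional figures are 6.1%, 5.4% and 4.6%.

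**Step 3: power at d = 0.75 for one two-sided paired test.**

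| Alpha | 16 completers | 19 | 24 | Completers for 80% |
|---|---|---|---|---|
| 0.05 (reproduces N = 16) | 0.80 | 0.87 | 0.94 | 16 |
| 0.05/3 (pairs within one subscale) | 0.62 | 0.73 | 0.85 | 22 |
| 0.05/4 = 0.0125 (split over subscales) | 0.57 | 0.69 | 0.82 | 24 |

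Also requiring a significant omnibus test can only lower these values.

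**The case against.** A reader might infer from the 14–19% that the plan carries that chance, in place of 5%, of wrongly reporting higher motivation under competition. The documents do not support this. That range counts any omnibus difference in any direction, including one between the two competition conditions. The hypothesis is directional, and section 6.1 follows the omnibus test with corrected pairs, so the matching event is the 3.5–5% one and its single-subscale comparator is 1.2%. Other readings of the undefined rule give 8–12% (one-sided pairs at 0.05/3) or 6.6–9.7% (one pooled competition-versus-feedback contrast at two-sided 0.05). All are below 14%.

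The plan may also hold more control than the text shows. Bold type may mark one subscale as primary; if so, the error-rate part largely falls away, while the basis of the power figure remains in question. If no IMI entry is bold, the case for strict control weakens. The four subscales also share one row with one post-hoc entry, so an appropriate correction could mean dividing by 12. That would bring the directional risk, without the omnibus gate, to 1.3–1.6%. The wording neither says this nor rules it out.

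Nor should Aim 2 simply be called underpowered: if all 24 enrolled complete a single session of about three hours, power at 0.05/3 is 0.85.

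All of this bears on the size of the problem. The missing decision rule, the missing divisor and the mismatch between 1.5 and 6.1 stand.

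**Conclusion.** The point holds as an unstated rule with a moderate, quantifiable effect. On the visible text, four subscales raise the chance of a false directional claim three- to fourfold, from about 1.2% to about 3.5–5%, and give about a 14–19% chance of some false omnibus condition effect. The first figure rests on the omnibus gate, a divisor of 3 and two-sided tests. Both rest on 0.05 per omnibus test and correlations between 0.7 and 0.

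The N of 16 is correct arithmetic for a test the plan does not contain. For corrected pairs, 80% power at 0.75 needs 22 completers, more than the 19 left after the planned attrition but fewer than the 24 enrolled. It cannot be concluded that no subscale was designated, because the bold type is not visible; the averaged effect size only suggests it. The change should be made before the data are analysed.

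**What to change.** First check the formatted table in section 6.1. Unless bold already marks one subscale as primary:

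- In 6.1, name one IMI measure that decides the Aim 2 motivation hypothesis at 0.05. Interest/Enjoyment is the subscale whose title shares a word with the hypothesis; a prespecified IMI composite would also serve, since the hypothesis mentions motivation too.
- In 6.1, report the remaining subscales as supportive with confidence intervals, Holm-adjusted if p-values are given.

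Whatever the bold shows:

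- In 6.1, state alpha, sidedness and the Bonferroni divisor (3 if all pairs within a measure are tested).
- In 1.5, restate the Aim 2 power for the test actually planned, and note that 0.75 is an average over subscales that need not apply to the chosen measure. A measure-specific value would have to come from the cited source; the documents do not give one.

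The cost is a few sentences in 6.1, one revised sentence in 1.5 and a look at the cited source, with no new data. The downside is that a result seen only on another subscale is no longer confirmatory.

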6.2 Data Security

Participant coding will be generated at Rutgers and stored by the PI on a security encrypted computer. De-identified data collected at Rutgers (on paper will be scanned, or digitally) will be uploaded by the PI or her designee to shared Box Account for this project. All paper data will be stored in locked file cabinet and digital data on a password protected computer. Consent forms will also be scanned and uploaded to a separate folder from the de-identified data. By the conclusion of the study all data will be stored in Box at the Rutgers site. Identifiers connected to the data will be destroyed once all the publications from the project are complete and grants have been submitted to extend the work. The project PI will make that determination. Data will not be stored at NYIT.

HRP-503a - TEMPLATE - Interventional Research Protocol 1.1.21
Protocol Title: Enhancing Exercise Intensity, Motivation and Enjoyment for Persons with PD (VCycle-Competition)

Protocol Version Date: v5 1.18.23; Protocol # - Pro2021001412

6.3 Data and Safety Monitoring

A. Data/Safety Monitoring Plan

The PI will monitor ongoing data collection, check actual participant files for recording accuracy, and monitor data entry for accuracy, including random checks throughout the duration of the study.

The research team will periodically evaluate the data collected regarding harms and benefits to determine whether subjects remain safe. Specifically, we will review the response to exercise (% of max heart rate and rate of perceived exertion) and the reports on the SSQ Cybersickness Questionnaires for every participant. This will be done by the study team led by the PI. At monthly research study meetings, we will discuss these variables. Minutes from the monthly safety minutes will serve to document this process. Any follow-ups with specific participants will be added to the monthly documentation. Any adverse events will be reported immediately to the IRB at both Rutgers and NYIT. Rutgers and NYIT will have a health monitor to verify the adherence to safety. Data monitoring will be overseen by an independent statistician who will receive quarterly reports on data management.

B. Data/Safety Monitoring Board Details

Statistician (Chair)	Professor and Dean School of Public Health, Rutgers University
Health Monitor	Associate Professor and Physical Therapist, School of Health Professions Rutgers University, JFK Medical Center

6.4 Reporting Results

A. Individual Subjects' Results

There is no plan to share individual results.

B. Aggregate Results

Summary of study findings will be shared with participants once published.

C. Professional Reporting

Study results will be disseminated at the appropriate conferences and published in the appropriate journals.

D. Clinical Trials Registration, Results Reporting and Consent Posting

Study will be registered as a clinical trial upon IRB approval.

6.5 Secondary Use of the Data

NA

7.0 Research Repositories – Specimens and/or Data

HRP-503a - TEMPLATE - Interventional Research Protocol 1.1.21

Protocol Title: Enhancing Exercise Intensity, Motivation and Enjoyment for Persons with PD (VCycle-Competition)

Protocol Version Date: v5 1.18.23;

Protocol # - Pro2021001412

Data will be stored for future research: (1) are the dependent variables from the study (2) to be stored in Synapse.Org.

8.0 Approvals/Authorizations

NA

